13.0 CRITERIA FOR REMOVAL FROM STUDY

The primary reasons for permanent treatment discontinuation are listed in **Table 4**.

Table 4. Primary Reasons for Permanent Treatment Discontinuation

Reason	Comment
Self-withdrawal (withdrawal of consent)	Patients may permanently discontinue study treatment and

	withdraw from the study at any time for any reason. Following study intervention discontinuation, patients should have protocol-required safety follow-up and long-term follow-up assessments unless the patient specifically declines further follow-up.
Adverse event or intercurrent illness or disease recurrence	Any intolerable adverse event (associated or not associated with the study intervention) that cannot be ameliorated by the use of adequate medical intervention or that, in the opinion of the principal investigator would lead to undue risk if study treatment were continued.
Gross noncompliance with protocol (violation)	The investigator may request permanent discontinuation of study treatment in the event of a major protocol deviation, lack of cooperation, or complete noncompliance.
Lost-to-follow-up	Reasonable effort should be made to contact any patient lost to follow-up during the course of the study in order to complete study-related assessments and record outstanding data.
Death	N/A

14.0 BIOSTATISTICS

14.1 Sample Size Calculation and Justification

This randomized phase trial will accrue 67 subjects with lung cancer over an accrual period of ~36 months. The primary analysis will compare the efficacy of different types of exercise training modalities, relative to progressive stretching (attention control group), on $\text{v}_{\text{O}_2\text{peak}}$. Three separate t-tests will be used to compare each exercise training arm to the attention-control arm in mean change across time for $\text{v}_{\text{O}_2\text{peak}}$. The overall alpha level will be controlled at a two-sided 0.05 by using Holm's procedure.⁵⁶ That is, Holm's procedure first ranks the three p-values from lowest to highest. The first (lowest) p-value has to be less than 0.05/3 (0.0167) to be significant and permit continuation to the other t-tests. The Holm's procedure continues sequentially in this fashion using alpha levels of 0.05/2 (0.025) and 0.05/1 (0.05) for the remaining two t-tests, respectively. Power for this study is defined as the probability that at least one of the three t-tests of the arm effect on $\text{v}_{\text{O}_2\text{peak}}$ is significant; in other words, power is the probability that the first of the 3 ordered t-tests are significant. We assume that change in $\text{v}_{\text{O}_2\text{peak}}$ will have a standard deviation of $3.0 \text{ mL}\cdot\text{kg}^{-1}\text{min}^{-1}$. Statistical power depends upon the configuration of mean change in $\text{v}_{\text{O}_2\text{peak}}$ across the 4 arms. Thus, for example, 80% power is obtained when the mean change in $\text{v}_{\text{O}_2\text{peak}}$ across Arms A, B, C, and D is 0.60, 0.60, 2.10, and 0.0 ($\text{mL}\cdot\text{kg}^{-1}\text{min}^{-1}$), respectively.

A final important consideration when conducting exercise RCTs, is extent of exercise 'drop-in' or contamination in Arm D. In other words, the concern is that patients assigned to attention control independently initiate an exercise training program which, in turn, potentially dilutes the efficacy of aerobic training on the outcomes of interest. However, we feel this is less of a concern in the present study because patients (in the exercise training arms) will be provided with supervised, individualized training prescriptions (which will be difficult to replicate without sophisticated prescription algorithms and expertise) and attention-control participants are also provided with a supervised attention intervention.

Nevertheless, we will carefully monitor the amount of exercise performed outside of the study in all study arms using subjective (i.e., self-report exercise logs) methods.

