1.0 PROTOCOL SUMMARY AND/OR SCHEMA

Primary Objective: To compare the efficacy of different types of exercise training modalities, relative to progressive stretching (attention control group), on exercise capacity (V02peak) in patients with lung cancer.

[figure not shown]
Design: Patients with Memorial Sloan Kettering Cancer Center (MSK) histologically-confirmed lung cancer will be randomized to one of the following four arms: **Arm A:** supervised aerobic training; **Arm B:** supervised resistance training; **Arm C:** supervised combined aerobic and resistance training; and **Arm D:** stretching (attention control group).

The goal of this RCT is to recruit a total of 160 patients with histologically-confirmed lung cancer at any stage or receiving any type of therapy. A total of 40 per arm patients will be randomized in a 1:1:1:1 ratio to the four study arms.

This RCT was initially initiated and conducted at Duke University Medical Center (DUMC) by the principal investigator ([name]). The trial was suspended at DUMC (protocol-independent) due to change of the PI's institution ([name] is now at MSK). At the time of trial suspension, a total of 93 participants had been randomly allocated to the four study arms: **Arm A** supervised aerobic training (n=24), **Arm B**: supervised resistance training (n=23), **Arm C**: supervised combined aerobic and resistance training (n=24), and **Arm D**: progressive stretching (attention control group) (n=22)

At MSK, patients will be enrolled and randomized until target enrollment is met (67 patients in total at MSK): **Arm A:** supervised aerobic training (n=16), **Arm B:** supervised resistance training (n=17), **Arm C:** supervised combined aerobic and resistance training (n=16), and **Arm D:** progressive stretching (attention control group) (n=18); At the end of the trial, data will be analyzed for the pre-planned sample size (n=160).

Figure 1. Study Schematic for MSK Recruitment

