14.2 Primary and Secondary End Point Analyses

14.2.1 Primary End Point Analysis: The primary analysis will compare the efficacy of different types of exercise training modalities, relative to progressive stretching (attention control group), on $\text{v}_{\text{O}_2\text{peak}}$ in lung cancer.

An intent-to-treat statistical analysis will be conducted. Baseline characteristics will be compared using the Fisher exact test for categorical variables or a Wilcoxon rank sum test for continuous variables. The primary end point comparison will be analyzed using a multiple linear regression model to test for differences among and between the study arms in $\text{v}_{\text{O}_2\text{peak}}$ from baseline to follow up. The multiple linear regression model will include the baseline value of $\text{v}_{\text{O}_2\text{peak}}$, the stratification variables (i.e., chemotherapy treatment and sex), and study site.

In the absence of evidence to the contrary, multiple imputation strategies for missing Week 17 $\text{v}_{02\text{peak}}$ data will be performed assuming data were missing at random using linear regression. Results will be aggregated over 20 imputed sets using the variance formula by Rubin. In addition, a per-protocol analysis will be performed using a multiple linear regression model to test for differences among and between the study arms in $\text{v}_{02\text{peak}}$ from baseline to the post-intervention assessment (Week 17) on the basis of exercise attendance and adherence to the supervised exercise training in Arms A to C (<80% versus 80%).

14.2.2 Secondary End Point Analyses: As for the primary end point, the intention-to-treat principle will be employed for analysis of all secondary end points. Multiple linear regression models will be used to test for differences among and between the study arms in secondary end points from baseline to the postintervention assessment (Week 17). The multiple linear regression model will include the baseline value of $\text{v}_{02\text{peak}}$, the stratification variables (i.e., chemotherapy treatment and sex), and study site.

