15.2 Randomization

Participants will be randomly allocated, on an individual basis, to one of the four study arms. Randomly allocated participants will remain in the same group for the entire duration of the intervention (i.e., no cross-over). To ensure randomized groups are similar at baseline, patient randomization will be stratified based on whether their lung cancer was operable or inoperable, prior treatment with chemotherapy (yes vs. no) and sex (male vs. female). Chemotherapy causes significant reductions in $\text{v}_{02\text{peak}}$, thus it is important for groups to be balanced on this factor. Similarly, male participants have higher $\text{v}_{02\text{peak}}$ than female

participants and therefore is also expected to influence the effect of exercise training on $VO_{2\text{peak}}$ and other endpoints, thus it is important to ensure that groups are also balanced on this variable.

A permuted block design with allocation weight of 1:1: 1:1 is used to generate the treatment assignments. Following the successful completion of all baseline assessments, ExOnc research team personnel will enter randomization criteria into REDCap. Upon confirmation of stratification factors (chemotherapy treatment and/or sex) REDCap will electronically randomized the patient. Written confirmation of group allocation will be provided by email, a copy of which will be placed in the patient's case report form. The primary study RSA will then inform the participant of their group allocation.

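### The 80% power in Section 14.1 does not follow from its own inputs: the stated t-tests with 40 per arm give about 76%, and no power is stated for the adjusted primary analysis.

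*Combined protocol and SAP*

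**What the plan says.** Section 14.1 describes the tests behind the power statement: "Three separate t-tests will be used to compare each exercise training arm to the attention-control arm in mean change across time" for VO2peak. Holm's procedure holds the overall two-sided alpha at 0.05, so the smallest of the three p-values is compared with 0.05/3 = 0.0167. Power is the probability that at least one test succeeds, or, in the plan's words, "power is the probability that the first of the 3 ordered t-tests are significant". The SD of change is taken as 3.0 mL/kg/min. The result is then given: "Thus, for example, 80% power is obtained when the mean change in" VO2peak is 0.60, 0.60, 2.10 and 0.0 in Arms A, B, C and D.

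Section 14.1 does not print the number per arm. The only count there is 67, which Sections 1.0 and 16.03 show to be the MSK remainder of the trial. Section 1.0 gives the full size: "A total of 40 per arm patients will be randomized in a 1:1:1:1 ratio to the four study arms", and "data will be analyzed for the pre-planned sample size (n=160").

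Section 14.2.1 specifies the analysis: "The primary end point comparison will be analyzed using a multiple linear regression model", with baseline VO2peak, the stratification variables (chemotherapy and sex) and study site as covariates. It also anticipates incomplete follow-up: "In the absence of evidence to the contrary, multiple imputation strategies for missing Week 17" VO2peak data are planned, using 20 imputed sets.

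**The concern.** This is the plan's only power figure, so a reader should be able to recover it from the printed inputs. Three things stand in the way.

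- With 40 per arm, the rule in 14.1 appears to give less than 80%.
- The calculation is for unadjusted t-tests, while the declared primary analysis is a covariate-adjusted regression.
- Section 14.1 makes no allowance for missing Week 17 values, although 14.2.1 expects some.

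What is at stake is how a null result would be read. If the true risk that no arm reaches significance is higher than the plan states, a negative trial is weaker evidence against the assumed effect than the plan implies.

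**Working it through.** **Inputs.** From 14.1: mean changes 0.60, 0.60, 2.10, 0.0; SD 3.0; three two-sided t-tests against Arm D; first threshold 0.05/3 = 0.0167; power = at least one test significant. From 1.0 and 4.2: 40 per arm. The 67 MSK patients alone (16/17/16/18) would give only about 35%, so 40 per arm is clearly the size meant.

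**Step 1: each comparison alone.** Standard error of a difference = 3.0 × √(2/40) = 0.671.

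| Comparison | Difference / SE | Power, t (78 df) | Power, normal |
|---|---|---|---|
| C vs D | 2.10/0.671 = 3.13 | 75.1% | 76.9% |
| A vs D, and B vs D | 0.60/0.671 = 0.894 | 6.5% each | 6.7% each |

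The normal critical value is 2.394, so for C vs D the power is Φ(3.130 − 2.394) = Φ(0.736) = 76.9%. Arm C carries almost all the power. A and B can add little, and because all three tests share Arm D they tend to succeed or fail together.

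**Step 2: at least one test significant.** Simulation of four normal arms with a shared Arm D (1 to 2 million replicates per run):

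| Version of the stated rule, 40 per arm | Power |
|---|---|
| Pairwise t-tests, as written | about 75.6% (repeat runs agree to about 0.1 point) |
| Error variance pooled over four arms | 76.4–76.5% |
| Normal approximation | 77.3–77.4% |

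None reaches 80%. The gap is 2.6 to 4.4 points, well beyond simulation error. The chance that no arm is significant is about 24%. As a separate quantity, the chance that Arm C itself is declared significant under the full Holm procedure is 75.3%.

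**Step 3: what would give 80%.** With pairwise t-tests:

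- an Arm C change of about 2.2 (2.20 gives 79.9%);
- an SD of about 2.85 (80.3%);
- about 44 per arm (80.2%; 43 gives 79.1%).

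**Step 4: where 80% may come from (not confirmed).** Treating the three tests as independent, with normal approximations, gives 1 − (1 − 0.7693) × (1 − 0.0674)² = 79.9%. That product is not valid with a shared control arm. The same shortcut with t distributions gives 1 − (1 − 0.7514) × (1 − 0.0653)² = 78.3%. Using 0.025 as the first threshold gives 80.5%, but this contradicts the printed 0.0167.

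**Step 5: missing data (extrapolation).** Section 16.02 reports 8 of 78 operable Duke patients lost, which is 10.3% (the section prints 12%). No completion figure is given for the 15 inoperable patients. If 10.3% held throughout, 40 × 70/78 = 35.9, or about 36 evaluable per arm, and the 14.1 rule gives about 70%. At 12% loss (35 per arm) it gives about 69%. Both assume that imputation from baseline covariates restores little information.

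**Step 6: the 14.2.1 regression (illustration only).** Assume equal variance at both visits and correlation ρ between baseline and follow-up. The variance of change is 2σ²(1 − ρ) = 9. The residual variance given baseline is σ²(1 − ρ²) = 9(1 + ρ)/2, so the residual SD is 3√((1 + ρ)/2). Simulating the full regression gives:

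| Chemotherapy, sex and site explain | Per arm | ρ = 0.6 | ρ = 0.8 | ρ = 0.9 |
|---|---|---|---|---|
| Nothing further | 40 | 85% | 80% | 78% |
| Nothing further | 36 | 81% | 75% | 73% |
| 10% of residual variance | 40 | 89% | 85% | 83% |
| 10% of residual variance | 36 | 85% | 80% | 78% |

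The documents give neither ρ nor the share explained, so they do not select a cell.

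**The case against.** The strongest reply is that the gap is small and concerns a test the trial will not use for its primary comparison. A 5% smaller SD (2.85), or an Arm C change of 2.2 instead of 2.1, restores 80%, and both inputs are assumptions. The set of means is offered only as an example. Powering on unadjusted tests and analysing with covariates is common practice, and with 40 per arm most of the illustrative values for the adjusted model are at or above 80%. Enrolment is fixed at 160, 93 of whom were randomized at Duke, so no design decision changes. The attrition figure extrapolates from operable patients at one site.

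Much of this stands, and it limits the weight of the point. The documents do not show that the primary analysis is underpowered, and the 36-per-arm figure is a sensitivity value only. It does not rescue the printed number. The wording makes the means an example, but the 80% attached to them is a definite claim, and no version of the stated rule yields it. Covariate adjustment may recover the difference, but the plan supplies nothing from which to show it.

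**Conclusion.** The point holds. Under 14.1's own rule, with 40 per arm and complete data, power is about 76% rather than 80%, and the risk that no arm is significant is about 24% rather than 20%. This rests on the printed means and SD, normal data, equal variances and the 40 per arm taken from Sections 1.0 and 4.2. Power for the adjusted regression in 14.2.1 is unknown and may fall on either side of 80%. Type I error, the estimand and trial conduct are untouched. The point should be fixed because this is the plan's only power figure, but it is not a reason to alter the trial.

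**What to change.** Restate Section 14.1 along these lines: with 160 randomized (93 at Duke plus 67 at MSK, 40 per arm), unadjusted t-tests at Holm's first threshold have about 76% power for mean changes of 0.6, 0.6, 2.1 and 0 with SD 3.0; 80% corresponds to an Arm C change of about 2.2.

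Two secondary additions would help:

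- Give about 70% at 36 evaluable per arm, labelled as a sensitivity figure under an assumed loss of about 10%.
- State the power of the 14.2.1 regression, with the assumed baseline/follow-up correlation or residual SD and its source.

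The cost is SAP wording only. Enrolment, tests, alpha and estimand stay as they are. The one drawback is a slightly less favourable stated power for the unadjusted tests.

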14.2 Primary and Secondary End Point Analyses

14.2.1 Primary End Point Analysis: The primary analysis will compare the efficacy of different types of exercise training modalities, relative to progressive stretching (attention control group), on $\text{v}_{\text{O}_2\text{peak}}$ in lung cancer.

An intent-to-treat statistical analysis will be conducted. Baseline characteristics will be compared using the Fisher exact test for categorical variables or a Wilcoxon rank sum test for continuous variables. The primary end point comparison will be analyzed using a multiple linear regression model to test for differences among and between the study arms in $\text{v}_{\text{O}_2\text{peak}}$ from baseline to follow up. The multiple linear regression model will include the baseline value of $\text{v}_{\text{O}_2\text{peak}}$, the stratification variables (i.e., chemotherapy treatment and sex), and study site.

In the absence of evidence to the contrary, multiple imputation strategies for missing Week 17 $\text{v}_{02\text{peak}}$ data will be performed assuming data were missing at random using linear regression. Results will be aggregated over 20 imputed sets using the variance formula by Rubin. In addition, a per-protocol analysis will be performed using a multiple linear regression model to test for differences among and between the study arms in $\text{v}_{02\text{peak}}$ from baseline to the post-intervention assessment (Week 17) on the basis of exercise attendance and adherence to the supervised exercise training in Arms A to C (<80% versus 80%).

14.2.2 Secondary End Point Analyses: As for the primary end point, the intention-to-treat principle will be employed for analysis of all secondary end points. Multiple linear regression models will be used to test for differences among and between the study arms in secondary end points from baseline to the postintervention assessment (Week 17). The multiple linear regression model will include the baseline value of $\text{v}_{02\text{peak}}$, the stratification variables (i.e., chemotherapy treatment and sex), and study site.

In the absence of evidence to the contrary, multiple imputation strategies for missing Week 17 end point data will be performed assuming data were missing at random using linear regression, as described above. Again, a per-protocol analysis will be performed using a multiple linear regression model to test for differences among and between the study arms in secondary end points from baseline to the post-intervention assessment (Week 17) on the basis of exercise attendance and adherence to the supervised exercise training sessions in Arms A to C (<80% versus 80%).

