Due to the presence of significant, and potentially clinically important, variability in CPET procedures (VO_{2peak} measurement), all potential participants will perform a second CPET at baseline to account for potential learning effects and variability.³⁰ If both the first and second CPET achieve acceptable test criteria, results of the second test will be used in all protocol procedures and statistical analyses.

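### Two baseline CPETs are planned because VO2peak is noisy, but the primary model adjusts for one value; the mean of the acceptable tests would give a modest gain in precision

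*Combined protocol and SAP*

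**What the plan says.** - **Two tests.** Section 12.1 says that "all potential participants will perform a second CPET at baseline to account for potential learning effects and variability". Table 1 (section 7.3, footnote 4) and Table 2 (section 8.0) say the same, and give important variability in the VO2peak measurement as a reason.
- **Timing.** Section 8.0 has the baseline assessments completed before randomisation.
- **Which test counts.** If both are acceptable, Table 2 takes the better one. Section 12.1 takes the second, for all procedures and analyses.
- **Model.** Section 14.2.1: "The multiple linear regression model will include the baseline value of" VO2peak, together with the stratification variables and study site. Missing Week 17 values are multiply imputed by linear regression. No section uses both baseline tests in the analysis.
- **Power.** Section 14.1: "The overall alpha level will be controlled at a two-sided 0.05 by using Holm's procedure", and "The first (lowest) p-value has to be less than 0.05/3 (0.0167) to be significant". It states that "80% power is obtained when the mean change in" VO2peak "across Arms A, B, C, and D is 0.60, 0.60, 2.10, and 0.0" mL/kg/min, assuming that the change "will have a standard deviation of" 3.0.
- **Size.** Section 1.0: "A total of 40 per arm patients will be randomized in a 1:1:1:1 ratio to the four study arms". Of the 160, 93 were randomised at the first site and 67 are to come from MSK.

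**The concern.** The plan names measurement noise as a problem and adds a maximal exercise test because of it. Its model then takes one noisy value where two may exist. In a baseline-adjusted regression, error in the baseline weakens the covariate and leaves more residual variance. Averaging two tests reduces that error. Both tests precede allocation, so conditioning on either or both cannot bias an arm contrast. What is at stake is power in a four-arm trial with 40 patients per arm and little margin, using data that the protocol already plans to collect.

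**Working it through.** **1. The plan's own figure.** Section 14.1 gives 40 per arm, SD 3.0, mean changes 0.60/0.60/2.10/0.0 and first-step alpha 0.05/3. The standard error of a contrast is 3.0 × √(2/40) = 0.671. Power is 76.9% for C against D and 6.7% each for A and B against D (normal approximation). Treated as independent, the three tests give 1 − (1 − 0.067)² × (1 − 0.769) = 79.9%, which matches the stated 80%. Allowing for the shared control arm, simulation gives 75.6-77.3%, depending on the test used. The stated power has no reserve, and it does not count any gain from baseline adjustment.

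**2. Residual variance.** Let ρ be the correlation of one baseline test with Week 17, and r the test-retest reliability. Neither is in the documents; I take ρ = 0.7-0.8 and r = 0.85-0.95. As a share of outcome variance, the residual is:
- one test (the section 12.1 rule): 1 − ρ²
- better of two (the Table 2 rule), equal test means: 1 − ρ²/[1 − (1 − r)/π]
- mean of two: 1 − 2ρ²/(1 + r)

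For ρ = 0.8 and r = 0.90:
- one test: 1 − 0.64 = 0.360
- better of two: 1 − 0.64/0.968 = 0.339
- mean of two: 1 − 1.28/1.90 = 0.326

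| ρ, r | One | Better | Mean | Fall vs one | Fall vs better |
|---|---|---|---|---|---|
| 0.7, 0.95 | 0.510 | 0.502 | 0.497 | 2.5% | 0.9% |
| 0.8, 0.90 | 0.360 | 0.339 | 0.326 | 9.4% | 3.7% |
| 0.8, 0.85 | 0.360 | 0.328 | 0.308 | 14.4% | 6.0% |

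Against one test, the ends of the range are worth 160 × (0.510/0.4974 − 1) = 4 and 160 × (0.360/0.3081 − 1) = 27 patients.

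**3. Power if all 160 have two tests.** Assume equal variances at baseline and Week 17. A change SD of 3.0 with ρ = 0.8 gives an outcome variance of 9/(2 × 0.2) = 22.5. At r = 0.90 the residual SD is √(22.5 × 0.360) = 2.85 with one test and √(22.5 × 0.3263) = 2.71 with the mean. Simulated first-step Holm power, with the shared control kept, goes from 81.3% to 85.3%.

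A second set of assumptions lets true change add variance at Week 17 (baseline SD 5, reliability 0.90). It gives 75.8% with the second test, 79.6% with the better test and 82.4% with the mean. At reliability 0.98 the three are 75.6%, 76.0% and 76.5%. Familywise error under the null stays near 4% throughout.

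**4. If only the 67 MSK patients have two tests.** The fall against one test is scaled by 67/160 = 0.419, so 2.5-14.4% becomes about 1-6%. At 0.8 and 0.90 it is 9.4% × 0.419 = 3.9%, the SD is 2.79 and power is 83.0% against 81.3%. A finite-sample simulation of the regression gives 79.6% rising to 81.5%. Against the better test, the averaged residuals are (93 × 0.360 + 67 × 0.3263)/160 = 0.3459 and (93 × 0.360 + 67 × 0.339)/160 = 0.3512, a fall of 1.5%.

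**5. Form of the covariate.** In that case, entering the two tests as separate covariates, with a constant and a missing indicator for one-test patients, recovers only about 0.1-2.6%. It forces one slope on the first test, where one-test patients need 0.80 and two-test patients 0.8/1.9 = 0.42. The mean of available tests needs slopes of 0.80 and 0.80/0.95 = 0.84, so pooling them loses little: simulation recovers 1.0-5.9%.

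**The case against.** The strongest reply is that nothing here is an error. Regression on one prespecified baseline is standard and unbiased, and section 12.1 makes a deliberate choice of the second test, with learning effects among its reasons. That stands: this is a point about efficiency. The constant learning effects tested (0.3 and 0.5 mL/kg/min) do not remove the gain.

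Three stronger readings are tempting, and the documents do not support them.
- **That every patient has two usable tests.** Section 6.1 requires only one acceptable CPET, and the selection rules are conditional on both being acceptable. No section records a second test for the 93 first-site patients (58% of 160). The reliability study cited for the repeat in Table 2 is dated 2015, after the September 2013 status report in section 16.02. That does not prove the second tests are absent, so the database must settle it.
- **That the largest gain applies whichever baseline rule is used.** The better-of-two rule already draws on both tests, so only about 1-6% remains against it.
- **That the change costs nothing.** It needs a rule for one-test patients and possibly one degree of freedom.

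The dependence on an unstated reliability also stands. If CPET repeats very closely, the gain is negligible.

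**Conclusion.** The point holds as a modest improvement in precision, not as a flaw in validity. The plan leaves an acceptable pre-randomisation measurement of its primary endpoint out of the adjustment. With two tests for all, residual variance falls about 2.5-14% against the second-test rule and about 1-6% against the better-test rule. With two tests at MSK only, it falls about 1-6% against a single test, or roughly 2 points of power at correlation 0.8 and reliability 0.90, and less against the better test. All these figures rest on an assumed correlation of 0.7-0.8 and reliability of 0.85-0.95. The direction is the same across the settings examined. The size depends mainly on how many first-site patients have a second test and on which baseline rule the sponsor meant.

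**What to change.** - In section 14.2.1, and in the imputation model, define the baseline covariate as the mean of all acceptable pre-randomisation CPET VO2peak values, using the single value where only one exists. No patient then leaves the intention-to-treat set for want of a second test.
- Add a one-test indicator only where it is not aliased with study site. If no first-site patient and every MSK patient has two tests, the indicator and the site term are the same column.
- Reconcile Table 2 with section 12.1 on which single test serves the other uses, such as eligibility, prescription and descriptive change.
- Confirm from the first-site database how many of the 93 patients have two acceptable tests, and fix the wording before outcomes are unblinded.

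The cost is a short text change and one database query. The mean replaces the single value one for one, so the model loses at most one degree of freedom, for the indicator. No further testing of patients is needed.
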